## 6.2 Visit 2 (Remote)– Week 2-3

- Procedural elements
  - Blood collection (CBC, electrolytes and/or VBG, liver function tests, kidney function tests)
  - Urine collection (same as section 6.1)
- Medication adherence questionnaire (appendix E): family to send this to us electronically or via mail.
- Interview elements
  - AE assessment
  - Concomitant medication review
  - Ongoing therapies (same as section 6.1)
- Dose Adjustment (see section 5.2) – After venous blood gas and electrolytes have resulted, partnering clinician will instruct patient/caregiver regarding administration of drug or placebo via phone call, telehealth, or in person.

### 6.3 Visit 3 (Remote)– Week 3-5

- Procedural elements
  - Blood collection (same as section 6.2)
  - Urine collection (same as section 6.1)
- Medication adherence questionnaire (appendix E): family to send this to us electronically or via mail.
- Interview elements
  - AE assessment
  - Concomitant medication review
  - Ongoing therapies (same as section 6.1)
- Dose Adjustment (see section 5.2) – After venous blood gas and electrolytes have resulted, partnering clinician will instruct patient/caregiver regarding administration of drug or placebo via phone call, telehealth, or in person.

### 6.4 Visit 4 (Remote)– Visit 3 +1-3 weeks

- Procedural elements
  - Blood collection (same as section 6.2)
  - Medication adherence questionnaire (appendix E): family to send this to us electronically or via mail.
- Interview elements
  - AE assessment
  - Concomitant medication review
  - Ongoing therapies (same as section 6.1)
- Dose Adjustment (see section 5.2) – After venous blood gas and electrolytes have resulted, partnering clinician will instruct patient/caregiver regarding administration of drug or placebo via phone call, telehealth, or in person. At this visit, the dose can only be adjusted downwards. If the dose needs to be adjusted, repeat CBC, electrolytes and/or VBG will be checked within 4 weeks of the dose adjustment. Repeat downward dose adjustments based on labs and repeat CBC + VBG or electrolytes will occur until either the dose does not need to be adjusted downwards or the subject is off therapy.

### 6.5 Visit 5 – Week 21-34

- Interview elements:
  - Concomitant medication review
  - Ongoing therapies (same as section 6.1)
  - Medication adherence questionnaire (see section 6.2)
  - AE assessment
- Procedural elements:
  - Physical exam (see section 6.1)
  - Mini-ICARS
  - PATA
  - NPCRS
  - Blood collection (see section 6.1) In addition, random blood level of acetazolamide will be collected.

- Urine collection (see section 6.1)
- Survey given to families to complete and returned to site at or after visit by mail or electronically
  - PROMIS
- Open Label Extension (OLE) or discontinuation – investigator will discuss with family option of rolling over into an open label extension of the study where the patient will receive the drug. If patient/caregivers decide to proceed with OLE, the patient will be started on dose 1 of acetazolamide.

## 6.6 Visit 6 (Remote)– Visit 5 +1-3 weeks

- Procedural elements
  - Blood collection (same as section 6.2)
  - Urine collection (same as section 6.1)
- \*Medication adherence questionnaire (see section 6.2)
- Interview elements
  - AE assessment
  - Concomitant medication review
  - Ongoing therapies (same as section 6.1)
- \*Dose Adjustment (see section 5.2) – After venous blood gas and electrolytes have resulted, investigator will instruct patient/caregiver regarding administration of drug via phone call, telehealth, or in person.

\* Will only be performed for those individuals who opted to continue in the OLE.

## 6.7 Visit 7 (Remote)– Visit 6 + 1-3 weeks

- Procedural elements
  - Blood collection (same as section 6.2)
  - Urine collection (same as section 6.1)
- \*Medication adherence questionnaire (see section 6.2)
- Interview elements
  - AE assessment
  - Concomitant medication review
  - Ongoing therapies (same as section 6.1)
- \*Dose Adjustment (see section 5.2) – After venous blood gas and electrolytes have resulted, investigator will instruct patient/caregiver regarding administration of drug via phone call, telehealth, or in person.

\* Will only be performed for those individuals who opted to continue in the OLE.

## 6.8 Visit 8 (Remote)– Visit 7 +1-3 weeks

- Procedural elements
  - Blood collection (same as section 6.2)
  - \*Medication adherence questionnaire (appendix E): family to send this to us electronically or via mail.

- Interview elements
  - AE assessment
  - Concomitant medication review
  - Ongoing therapies (same as section 6.1)
- \*Dose Adjustment (see section 5.2) – After venous blood gas and electrolytes have resulted, partnering clinician will instruct patient/caregiver regarding administration of drug or placebo via phone call, telehealth, or in person. At this visit, the dose can only be adjusted downwards. If the dose needs to be adjusted, repeat CBC, electrolytes and/or VBG will be checked within 4 weeks of the dose adjustment. Repeat downward dose adjustments based on labs and repeat CBC + VBG or electrolytes will occur until either the dose does not need to be adjusted downwards or the subject is off therapy.

\* Will only be performed for those individuals who opted to continue in the OLE.

## 6.9 Visit 9 – Week 49-105

- Interview elements:
  - Concomitant medication review
  - Ongoing therapies (see section 6.1)
  - \*Medication adherence questionnaire (see section 6.2)
  - AE assessment
  - Reason for discontinuation of study treatment and discontinuation of study
- Procedural elements:
  - Physical exam (see section 6.1)
  - Mini-ICARS
  - PATA
  - NPCRS
  - Blood collection (see section 6.1)
  - Urine collection (see section 6.1)
  - Annual screening ophthalmological exam including intraocular pressure testing.
- Survey given to families to complete and returned to site at or after visit by mail or electronically
  - PROMIS

## 6.10 Visit – Early Termination

- Procedural elements
  - Blood collection (same as section 6.1)
  - Urine collection (same as section 6.1)
- Medication adherence questionnaire (see section 6.2)
- Interview elements
  - AE assessment
  - Concomitant medication review
  - Ongoing therapies (same as section 6.1)
  - Reason for discontinuation of study treatment and discontinuation of study

- Study withdrawal – investigator will discuss with the patient and caretakers the reason for withdrawal from the study. Investigator will also attempt to consent/assent subject and/or caretaker family to collect follow up information whenever possible through review of medical records. Data to be collected include lab data to look at urinalysis values, chemistries in serum, hematology, physical exam data (including vital signs and reviewing concomitant medications), ICARS scoring, NPCRS scoring and any other adverse events if available. These evaluations will be obtained as part of their clinical care.

Table 3: Schedule of Events	Visit 1 (Wk 0)	Visit 2 (Wk 2-3)	Visit 3 (Wk 3-5)	Visit 4 (Visit 3 + 1-3 wks)	Visit 5 (Wk 21-34)	Visit 6 (Visit 5 + 1-3 wks)	Visit 7 (Visit 6 + 1-3 wks)	Visit 8 (Visit 7 + 1-3 wks)	Visit 9 (Wk 49- 105)	Early Withdrawal
Informed Consent	x									
Medical History	x									
Clinical History	x									
Physical Exam*	x				x				x	
HC	x			x	x			x	x	
Height	x			x	x			x	x	
Weight	x			x	x			x	x	
Vital Signs (Temperature, BP, RR, HR)	x				x				x	
Ophthalmological exam including intraocular pressure testing**									x	
NPCRS a	x				x				x	
Mini-ICARS b	x				x				x	
PATA	x				x				x	
Blood c collection	x	x	x	x	x	x	x	x		x
Urine d Collection	x	x	x		x	x	x		x	
PROMIS e	x				x				x	
I/E review; Randomization	x									
Dose Initiation	x									
Dose Adjustment		x	x	x		x	x	x	x	
Open label continuation or discontinuation					x					x
Medication adherence questionnaire		x	x	x	x	x	x	x		x
AE Assessment		x	x	x	x	x	x	x		x
Concomitant Medication Review	x	x	x	x	x	x	x	x		x
Ongoing therapies (PT, OT, ST, FT) f	x	x	x	x	x	x	x	x		x

aAppendix A bAppendix B cBlood labs: see sections 6.1 and 6.2 dUrine labs: see section 6.1. ePROMIS: Subset of patient reported outcomes as for natural history trial based on PROMIS questionnaire. See Appendix C. fPT = physical therapy, OT = occupational therapy, ST = speech therapy, FT = feeding therapy – collecting information regarding if

		therapy ongoing (yes/no), number sessions per month. Grey shading: only for subjects who continue in OLE.*head circumference, height, and weight will be measured at least every 12 weeks. **to be done offsite as part of routine clinical care. Abbreviations: Wk = week, I/E inclusion and exclusion criteria, HC = head circumference, BP = blood pressure, RR = respiratory rate, HR = heart rate
--	--	---

## 7 Statistical Plan

### 7.1 Sample Size Determination

Given that the improvement in ICARS, which is highly correlated to the Mini-ICARS, was 5.6 points over roughly 20 months (Serrano, 2015), if we assume a linear change, then we have  $5.6*(6/20) = 1.68$  points decrease over 6 months. The expected effect size in the experimental group is 6 points decrease, whereas it is 1.68 in the placebo. Using a standard deviation of the change in scores of 4, two-sided alpha 0.05, and power 75%, the sample size required to detect a true difference of 4.32 units is 26 patients total (13 per arm) based on the two-sample t-test.

### 7.2 Statistical Methods

#### Descriptive Statistics

Univariate descriptive statistics and frequency distributions will be calculated, as appropriate for all variables. Baseline values for demographic, clinical, and outcome variables (primary and secondary) will be tabulated for the treatment groups. These analyses will help identify potential confounding variables to be used as covariates in sensitivity analyses. Distributions across subgroups used in randomization will be qualitatively compared to assess whether the randomization was successful in equalizing distributions of these prognostic variables across treatment groups. Putative prognostic variables that will be investigated through these descriptive analyses include variables such as sex, baseline Mini-ICARS score, age, and baseline NPCRS score.

#### Primary Endpoint Analysis Approach:

**Primary Hypothesis:** The administration of acetazolamide will improve the ataxia symptoms in patients with PMM2-CDG. **Primary Endpoint:** Change in Mini-ICARS score from baseline to 6 months.

The primary analysis will be conducted using the full analysis set (see Section 7.3). The between-arm mean difference in the change in Mini-ICARS score from baseline to 6 months will be evaluated via a two-sample t-test. The primary analysis will include all patients with a baseline and 6-month Mini-ICARS score. As a sensitivity analysis, all patients with a missing Mini-ICARS score at 6 months will be assumed to have no change in Mini-ICARS score between baseline and 6 months. A per-protocol analysis will also be conducted using the per-protocol set (see Section 7.3). A nominal significance level of  $\alpha=0.05$  will be used for all analyses.

**Exploratory Analysis:** To explore characteristics of individuals with PMM2-CDG who do not respond to acetazolamide (objective 4), we will define the subgroup of individuals who received at least 6 months of acetazolamide and did not have an improvement in ataxia. These individuals could have received acetazolamide during either the blinded period or open label extension period for at least 6 months. In addition, their Mini-ICARS score difference after being on acetazolamide for at least six months was at or less than the mean Mini-ICARS score change for the placebo group. A correlation analysis for change in Mini-ICARS from baseline to 6 months will be performed with each of the baseline characteristics. These baseline characteristics include age, sex, weight, height, head circumference, NPCRS score, Mini-ICARS score, PATA score, concomitant medication list, allergies, current ability with activities of daily living, laboratory

data (carbohydrate deficient transferrin results (Mono/Di, A/Di, Apo CIII1/Apo C III2, Apo CIII0/Apo CIII2), electrolytes (Na, K, Cl, CO2), VBG (pH, pCO2, PO2, CO2, Base excess) or bicarbonate/CO2, liver function tests (AST, ALT, GGT, indirect and direct bilirubin, total protein, albumin, alkaline phosphatase), kidney function tests (BUN, Creatinine, Urinalysis, urine calcium/creatinine ratio, urine protein/creatinine ratio)), growth (height, weight, head circumference), vital signs (blood pressure, respiratory rate, heart rate), ongoing therapies (physical, occupation, speech therapy yes/no and sessions/month), physical exam elements (normal/abnormal for each examined system including neurologic exam, cardiovascular exam, abdominal exam, HEENT exam, dermatologic exam, pulmonary exam), prior or existing medical conditions within the standard body systems (present/absent – general, dermatologic, HEENT, cardiovascular, respiratory, GI, GU, musculoskeletal, neurologic, allergic, immunologic, hematologic, endocrine), and number of past hospitalizations.

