Statistical Methodology	
The primary analysis will be conducted using the full analysis set, defined as all randomized patients who complete the baseline and 6-month visits. The between-arm mean difference in the change in Mini-ICARS score from baseline to 6 months will be evaluated via a two-sample t-test. The primary analysis will include all patients with a baseline and 6-month Mini-ICARS score.

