### 5.3 Method for Assigning Subjects to Treatment Groups

- After informed consent, randomization will occur as a tiered approach based on age (group 1 <12 years, group 2 ≥ 12 years) and Mini-ICARS score (group a score <25, group b ≥ 25 points) to give 50/50% to placebo/drug, respectively. If a Mini-ICARS was performed and recorded <1 year prior to enrollment, randomization can be based on that historic score. The randomization scheme will be generated by a statistician that is not part of the study team and will be provided to the applicable research pharmacy.

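### The primary t-test on change is valid but ignores Visit 1 Mini-ICARS and age; a pre-specified adjusted model would gain roughly 0 to 5 points of power, or lose 1 to 3 if neither predicts change

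*Combined protocol and SAP*

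**What the plan says.** The primary endpoint is change in Mini-ICARS over the blinded period (section 3.4). Section 7.2, Primary Endpoint Analysis Approach, states: "The between-arm mean difference in the change in Mini-ICARS score from baseline to 6 months will be evaluated via a two-sample t-test". The Study Summary says the same, and section 7.1 sizes the trial on that test: the required number "is 26 patients total (13 per arm) based on the two-sample t-test".

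Three other places bear on the choice.

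- **Section 5.3.** "randomization will occur as a tiered approach based on age" (under 12 years, or 12 and over) and on Mini-ICARS (under 25, or 25 and over). Where a score less than a year old exists, "randomization can be based on that historic score". The scheme "will be provided to the applicable research pharmacy"; the text does not say whether there is one study-wide list or one per site.
- **Section 7.2, Descriptive Statistics.** Baseline values are tabulated by treatment group, and "These analyses will help identify potential confounding variables to be used as covariates in sensitivity analyses". Under "Putative prognostic variables that will be investigated through these descriptive analyses" it names sex, age, and baseline Mini-ICARS and NPCRS.
- **Section 7.2, Secondary Endpoint Analysis Approach.** The secondary scores, including NPCRS and PATA, are analysed by regressing the 6-month value on the baseline value and arm.

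The named alternatives for the primary endpoint (zero-change imputation and the per-protocol analysis) have no covariates.

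**The concern.** The plan treats age and baseline severity as prognostic when it randomizes and when it describes the sample, then leaves both out of the primary analysis. Two things are at stake.

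**Precision.** Planned power is only 75%, with accrual capped at 33 (section 3.2). If either variable predicts change in both arms, a test that ignores it leaves explainable variation in the error term. Because randomization is stratified on these variables, the t-test then also becomes conservative.

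**Pre-specification.** With 13 per arm some baseline imbalance will remain, more so if lists are kept by site or historic scores are used to stratify. If covariates are chosen after the baseline tables by arm are seen, a gap between the adjusted and unadjusted results will be hard to interpret.

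**Working it through.** **Inputs from section 7.1:** difference 6 − 1.68 = 4.32 points; SD of change 4; two-sided alpha 0.05; 13 per arm.

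**Step 1. The plan's own figure.** The noncentrality is 4.32 / (4 × √(2/13)) = 4.32 / 1.569 = 2.753 on 24 df, giving power of 75.2%. With 12 per arm it is 71.5%, so 13 is the smallest number that reaches 75%. Allowing for 20% loss, 26 / 0.8 = 32.5, which rounds up to 33. Both figures agree with the plan.

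**Step 2. Adjusted model, ideal case.** If the covariates have within-arm correlation r with change, the residual SD is 4√(1 − r²). With both covariates in the model there are 22 df. With perfect covariate balance:

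- r = 0: noncentrality 2.753, power 74.9%
- r = 0.2: residual SD 3.919, noncentrality 2.810, power 76.6%
- r = 0.4: residual SD 3.666, noncentrality 3.004, power 81.9%

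Real balance is imperfect, which raises the variance of the adjusted estimate, so simulation is needed.

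**Step 3. Simulation under stratified randomization.** There were 26 patients and 24,000 trials per case (Monte Carlo error about 0.3 points). Here r is the correlation of baseline Mini-ICARS with change, and age has no effect. Assumed, because the documents do not state them: blocks of 4 within the four strata; in the uneven case, sites of 50/30/20%, strata of 65/35, and every patient stratified on a historic score correlated 0.8 with Visit 1. Power in %, t-test vs model with baseline and age:

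| r | One study-wide list | Three equal site lists | Uneven site lists, historic scores |
|---|---|---|---|
| 0 | 75.2 vs 73.9 | 74.5 vs 72.0 | 74.2 vs 71.9 |
| 0.2 | 75.4 vs 75.6 | 74.5 vs 73.9 | 74.7 vs 73.8 |
| 0.3 | 75.5 vs 77.5 | 74.9 vs 76.4 | 74.6 vs 75.5 |
| 0.4 | 76.1 vs 81.0 | 74.5 vs 79.4 | 74.6 vs 79.2 |

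Break-even is near r = 0.2 with one list and about 0.25 with site lists. Further runs (100,000 trials per setting, blocks of 2 or 4, even or uneven strata, covariates correlated or not) gave changes of −1.9 to −2.2 points at r = 0, −0.3 to −0.7 at 0.2 and +4.2 to +4.5 at 0.4. With no stratification at all the cost at r = 0 would be about 4 points, but that is not the plan.

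**Step 4. Type I error, one list.** For the t-test it is 5.1, 4.9, 4.3 and 4.0% at r = 0, 0.2, 0.3 and 0.4. For the adjusted model it is 4.8 to 5.2%.

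**Step 5. Mean 95% CI width, one list, t-test vs adjusted.** 6.42 vs 6.52 (r = 0), 6.44 vs 6.24 (r = 0.3), 6.44 vs 5.99 (r = 0.4).

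**Step 6. What r might be.** Suppose the score SD is s at both visits and the correlation between visits is ρ. Then 2s²(1 − ρ) = 16, so the covariance of baseline with change is −s²(1 − ρ) = −8. In absolute value, r = 8 / (4s) = 2/s. A baseline SD of 10 points gives 0.2; an SD of 5 gives 0.4.

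**Step 7. Other cases.**

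- Change also differs by an assumed 2 points between age strata: adjustment adds 0.8, 2.5 and 4.7 points at r = 0, 0.2 and 0.3 with one list, or 0.1, 1.6 and 3.9 with uneven site lists.
- Baseline predicts change only on drug: the effect is 0.0 (r = 0.3) to +1.2 points (r = 0.5) with one list, and −1.7 to +0.3 with uneven site lists.

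**The case against.** The strongest reply is that nothing here is wrong. Endpoint, test and sample size agree with one another, and type I error does not exceed its nominal level.

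The benefit also rests on an r that the documents do not supply. Section 4.1 admits any score above zero from age 4, so the baseline spread may be wide and r low, and at r = 0.2 the gain is nil. The one supporting observation, larger gains with higher baseline scores (section 1.3), comes from an uncontrolled treated group; if the relation holds only on drug, adjustment does almost nothing. Stratification already limits imbalance, and a covariate choice made late can touch only a sensitivity analysis. On this view one sentence naming the covariates in advance would be enough.

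Most of this stands as a limit on size: a power gain is possible, not established, and the site-list scenarios are assumptions. It does not remove the point. The sensitivity model is still unspecified, no reason is given for treating the primary score differently from the secondary scores, and the loss if the covariates turn out useless is small and known. Naming covariates for the sensitivity analysis alone would settle pre-specification but recover no power.

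**Conclusion.** The concern holds as a matter of efficiency and pre-specification, not as an error in the primary test. Across r from 0 to 0.4, adjusting for Visit 1 Mini-ICARS and age moves power from a loss of 1 to 3 points, through about zero near r = 0.2, to a gain of about 5.

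This rests on the plan's SD of 4 and difference of 4.32, on stratified randomization with an assumed block size, and on r read as the joint within-arm correlation of the covariates with change. If two independent covariates each had that correlation, the gain would be about 1 point at 0.2 and about 11 at 0.4. The change is worth making; confidence in the size of the gain is moderate because r is unknown.

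**What to change.** Before unblinding:

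1. In section 7.2 (Primary Endpoint Analysis Approach) and the Study Summary, replace the t-test sentence with wording such as: *The primary analysis will be a linear regression of 6-month Mini-ICARS on treatment arm, Visit 1 Mini-ICARS (continuous; the Visit 1 value even where a historic score was used to stratify) and age stratum (<12, ≥12 years). The adjusted mean difference will be reported with its 95% CI. The two-sample t-test on change will be a supportive analysis.*
2. In Descriptive Statistics, state that no covariate enters the primary model because of observed imbalance.
3. In section 7.1, state that 26 was derived from the unadjusted test and is kept.
4. In the Primary Endpoint Analysis Approach and Handling of Missing Data, state that the zero-change analysis sets a missing 6-month score equal to the Visit 1 score and uses the same model.

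The endpoint in section 3.4 can stay. With the Visit 1 score in the model, regressing the 6-month score or the change shifts only the baseline coefficient, by 1; treatment effect and standard error are identical. On a made-up data set of 33 patients with 7 missing scores, both forms gave −3.501 (SE 1.211).

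The cost is a few sentences, two degrees of freedom and no new data. If neither covariate predicts change, power falls by about 1 to 2 points with one study-wide list, and by up to about 3 with site lists or poor balance. If the sponsor keeps the t-test as primary, the covariates and model for the adjusted sensitivity analysis should at least be fixed now.

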### **Objective 4 (Secondary):**

**To explore characteristics of individuals with PMM2-CDG who do not respond to acetazolamide.**

In addition to analyzing our data for effect, we will perform subgroup analysis based on genotype, ataxia severity, baseline NPCRS score, sex, concomitant therapies, results of transferrin isoform analysis, concomitant medical problems/diagnoses, number of previous hospitalizations, ages at diagnosis, baseline laboratory test results, age at developmental milestones achievement, baseline developmental/educational achievement, baseline frequency and type of therapies, and baseline support needed for activities of daily living to determine if there are particular subgroups that are less responsive to therapy.

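### Objective 4's exploratory non-responder rule joins two conditions without a sign convention, so it is either contradictory or makes its placebo cutoff redundant, and the accompanying correlation has no placebo contrast

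*Combined protocol and SAP*

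**What the plan says.** Objective 4 (Section 2) is a secondary objective. It promises subgroup analyses "to determine if there are particular subgroups that are less responsive to therapy". Section 7.2 implements it in the Exploratory Analysis paragraph under the primary endpoint, in four sentences:

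- The subgroup is those who "received at least 6 months of acetazolamide and did not have an improvement in ataxia".
- Either period counts: "These individuals could have received acetazolamide during either the blinded period or open label extension period for at least 6 months".
- A second condition is joined to the first by the words in addition: the on-drug score difference qualifies if it "was at or less than the mean Mini-ICARS score change for the placebo group".
- For predictors: "A correlation analysis for change in Mini-ICARS from baseline to 6 months will be performed with each of the baseline characteristics".

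Section 7.1 supplies the direction and the expected values: "The expected effect size in the experimental group is 6 points decrease, whereas it is 1.68 in the placebo". A fall in score is therefore an improvement, and the placebo arm is expected to improve.

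**The concern.** The second condition is introduced as an addition to the first, so as written both must hold. The sign of the score difference is not defined, and with an improving placebo arm neither sign makes both conditions do any work. One sign leaves nobody in the group; the other makes the comparison with placebo irrelevant. A rule of improving no more than the placebo mean, which the second condition seems to aim at, is what neither version delivers. If this is left open, the definition will be settled after unblinding.

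The correlation is a separate problem. Objective 4 asks who responds less to therapy, which concerns the treatment effect. A correlation of change with a baseline characteristic, without reference to placebo, describes who changes and not why. Section 1.3 reports larger gains in patients with higher baseline ICARS in a pilot without a control group. This analysis could repeat that pattern and still leave its cause unknown, although this trial has a randomised placebo arm.

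**Working it through.** **Inputs.** From Section 7.1: mean improvement 6 points on acetazolamide and 1.68 on placebo, SD of change 4, 13 per arm, two-sided alpha 0.05. Assumptions: normal changes; for the 26-patient pool, every placebo-first patient enters the extension and responds as the active arm does.

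**1. The plan's own figure.** 5.6 × 6/20 = 1.68, and 6 − 1.68 = 4.32. The exact two-sample t-test has 75.2% power at 13 per arm and 71.5% at 12. The stated 26 patients are reproduced, so these values can be used to test the rule.

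**2. Logic.** Let D be the on-drug score minus the pre-drug score, I = −D the improvement, and M the placebo mean improvement.

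- Signed change: D ≥ 0 and D ≤ −M. With M = 1.68 no value satisfies both.
- Points of improvement: I ≤ 0 and I ≤ M. With M = 1.68 the first implies the second, so the cutoff removes nobody.
- Placebo reference alone: I ≤ M.

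The first two results need M > 0. The standard error of M is 4/√13 = 1.109, so P(M ≤ 0) = Φ(−1.68/1.109) = Φ(−1.51) = 0.065. In those trials the signed rule keeps patients between no change and the placebo worsening, and drops those who worsened most.

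**3. Size of the group.**

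- No improvement: Φ((0 − 6)/4) = Φ(−1.5) = 0.0668; × 13 = 0.87; × 26 = 1.74.
- At or below a placebo mean of exactly 1.68: Φ(−4.32/4) = Φ(−1.08) = 0.140; × 13 = 1.82; × 26 = 3.64.
- The same, allowing for sampling error in M: Φ(−4.32/√(16 + 16/13)) = Φ(−1.04) = 0.149; × 13 = 1.94; × 26 = 3.87.

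Simulation at the same values, with M estimated from 13 placebo patients:

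| Rule | Mean of 13 | Empty, active arm only | Empty, pool of 26 |
|---|---|---|---|
| Joint, signed change | 0.01 | 99% | – |
| Joint, improvement | 0.86 | 41% | 17% |
| At or below placebo mean only | 1.93 | 17% | about 5% |

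If changes are rounded to whole points (an assumption), the signed group is empty in 97.4% of trials, the joint improvement rule averages 1.07 of 13 and the single criterion 1.97. On the improvement scale the cutoff alters the group in only 1 to 2% of trials. If the true placebo change were zero, contrary to Section 7.1, the signed group would be empty in 78.6% of trials and the cutoff would alter the improvement-scale group in 20.1% (both with rounding).

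**4. The correlation.** For patients randomised to placebo, the baseline-to-6-month interval is entirely off drug. For the active arm alone, change combines drug response with prognosis and regression to the mean. Baseline Mini-ICARS is itself one of the listed characteristics, and it forms part of the change score it would be correlated with. The placebo mean enters only the non-responder cutoff, never the correlation. Section 7.2 gives no other method for the subgroup aim.

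**5. Precision of an interaction model.** Taking a residual SD of 4, the standard error per SD of a numeric characteristic is √2 × 4/√12 = 1.63 points (simulated mean 1.82 with the baseline score in the model). With t(21) = 2.08, the 95% CI is about ±3.4 to ±3.8 points. For a binary characteristic split 6/7 in each arm, the standard error is 4 × √(1/6 + 1/7 + 1/6 + 1/7) = 3.15.

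**The case against.** The best defence is that this is loose wording. The first sentence names a concept, no improvement on drug, and the later one can be read as giving its cutoff. Nobody would apply the signed version, because its cutoff alone would label about 86% of treated patients, the improvers, as non-responders. On the improvement scale the joint rule still gives a coherent group, those who did not improve. With 13 patients the choice moves the group by about one person.

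Much of this stands. A reader might infer that the rule can never identify anyone; the documents do not support that, since one reading gives a usable group. A reader might also take 41% as the chance of finding no non-responder under that reading. That figure covers the active arm alone, whereas Section 7.2 counts both periods; on a pool of 26 it is 17%. It is also fair that removing the no-improvement condition would rest on inferred intent, so the sponsor has to choose. What remains is that the text states both conditions, gives no sign, and includes a placebo cutoff that under the coherent reading almost never matters.

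On the correlation, the objection is that an interaction model in 26 patients is too imprecise to identify a subgroup: its interval of ±3.4 to ±3.8 points compares with a planned effect of 4.32. That is true. But the interaction estimates the quantity Objective 4 asks about and shows its uncertainty, whereas the correlation estimates something else.

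**Conclusion.** The point holds as a defect of definition and method in an exploratory analysis. At the planning values the rule is contradictory on signed change (active-arm group empty in about 97 to 99% of trials). On points of improvement the cutoff is redundant, leaving about 0.9 of 13 patients, or 1.7 of 26 if all placebo-first patients are treated and respond alike. Improving no more than the placebo mean would give about 1.9 and 3.9. These results depend on the placebo arm improving on average, which Section 7.1 assumes. The correlation cannot identify subgroups that respond less to therapy, whichever population it uses.

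Two further inferences would go too far. The primary t-test and sample size are not affected. Nor do the scheduling conflicts cause this defect: Visit 5 is at week 21-34 in Section 6.5 but week 40-56 in Section 5.7.1, and Visit 9 may fall at week 105 in Section 6.9 against about 1.75 years of participation in Section 3.3. Those are trial-wide and should be reconciled as a separate point.

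**What to change.** Amend the Exploratory Analysis text before unblinding:

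1. **Improvement.** Define it as the pre-drug score minus the on-drug score: Visit 1 to 5 for the active arm, and Visit 5 to 9 for placebo-first patients in the extension. Report the latter separately, because their comparator is a blinded-phase mean. For active-arm patients who continue, use Visit 1 to 5 only, for consistency.
2. **One criterion.** If a placebo reference is intended, use improvement at or below the placebo arm's mean Visit 1 to 5 improvement. If not, keep no improvement and drop the placebo cutoff.
3. **Predictors.** In the full analysis set, model the 6-month Mini-ICARS score on baseline score and arm, as Section 7.2 already does for secondary endpoints, plus the characteristic and its interaction with arm. Limit this to a short pre-named list. The putative prognostic variables under Descriptive Statistics, which "include variables such as sex, baseline Mini-ICARS score, age, and baseline NPCRS score", are one option; genotype, named in Objective 4, could be added if its groups are large enough. For baseline Mini-ICARS only the interaction term is new. Report exploratory estimates with CIs, and describe the other characteristics without tests.

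The cost is SAP wording; the Visit 1, 5 and 9 scores are already scheduled. Two limits should be stated: interaction precision is low, and about 14% of treated patients would fall at or below the placebo mean by chance even if the drug effect were identical in everyone. The non-responder group should be read descriptively.
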